Study Protocol

Official Title:

Clinical Evaluation of Kinesio Taping Outcomes in Stage II Cellulite: A Pilot Randomised Controlled Trial

NCT Number:

NCTXXXXXXX

Document Date:

September 16, 2025

Sponsor/Collaborator:

Klaipėda State University of Applied Sciences (Klaipėdos valstybinė kolegija)

Background

Cellulite is a common skin condition characterized by dimpling and uneven surface texture, primarily affecting women. It is associated with changes in the dermis and subcutaneous tissue, impaired microcirculation, and lymphatic congestion. Kinesio taping is a physiotherapy technique that may improve microcirculation and skin structure, but evidence for its effectiveness in cellulite is limited.

Objectives

The primary objective of this pilot randomised controlled trial is to evaluate the effects of kinesio taping on dermis density and low echogenic band (LEB) thickness in women with stage II cellulite. Secondary objectives include assessing changes in thigh circumference, body composition, cellulite stage, and skin moisture.

Study Design

This is a two-arm, parallel-assignment, open-label, randomised controlled trial.

Participants are allocated to either an experimental group (kinesio taping) or a control group (no intervention).

Participants

Eligible participants are women aged 18–45 years with stage II cellulite and normal body mass index (BMI). Exclusion criteria include pregnancy, edema, obesity, thrombosis, and skin infections.

Intervention

Experimental group participants receive kinesio taping once weekly for four consecutive weeks. Fan-shaped elastic tape is applied with 0–15% tension to the buttocks and thighs at standard anatomical points (gluteus maximus, posterior thigh, anterior thigh). Control group participants do not receive any intervention during the study period.

Outcome Measures

Primary Outcomes:

- Change in dermis density (measured by high-frequency ultrasound, DermaLab Combo 4).
- Change in low echogenic band (LEB) thickness (measured by ultrasound).

Secondary Outcomes:

- Change in thigh circumference (20 cm below the greater trochanter).
- Change in body composition (fat percentage, fat mass, fat-free mass, basal metabolic rate, total body water).
- Change in cellulite stage (Nürnberg-Müller Scale, Callegari Soft Plus).
- Change in skin moisture (Callegari Soft Plus device).

Sample Size

A total of 38 participants were enrolled, with randomisation into two groups (n=17 experimental, n=17 control). Sample size was determined using power analysis for an independent t-test, accounting for a 10% dropout rate.

Statistical Analysis

Data will be analysed using SPSS v25.0. Statistical tests include independent t-tests, paired t-tests, and effect size calculations (Cohen's d, Hedges' g). Significance is set at $p<0.05$.

Ethical Approval

The study was approved by the institutional ethics committee on 27 December 2024 (Nr. SSV6-114). All participants provided written informed consent.

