Statistical Analysis Plan (SAP)

Official Title:

Clinical Evaluation of Kinesio Taping Outcomes in Stage II Cellulite: A Pilot Randomised Controlled Trial

NCT Number:

NCTXXXXXXX

Document Date:

September 16, 2025

Sponsor/Collaborator:

Klaipėda State University of Applied Sciences (Klaipėdos valstybinė kolegija)

1. Introduction

This Statistical Analysis Plan (SAP) describes the planned analyses for the pilot randomised controlled trial evaluating the effects of kinesio taping on women with stage II cellulite. The SAP defines analysis populations, statistical methods, and reporting conventions in accordance with best practice guidelines.

2. Study Objectives

Primary Objectives:

- To evaluate the effect of kinesio taping on dermis density.
- To evaluate the effect of kinesio taping on low echogenic band (LEB) thickness.

Secondary Objectives:

- To assess changes in thigh circumference, body composition, cellulite stage, and skin moisture.
- To explore persistence of effects at 4 weeks post-intervention.

3. Study Design

This is a two-arm, open-label, parallel-assignment randomised controlled trial with an experimental group (kinesio taping) and a control group (no intervention).

4. Analysis Populations

The primary analysis will be conducted on the intention-to-treat (ITT) population, including all randomised participants who completed at least baseline and one follow-up measurement. Per-protocol analyses may be conducted excluding participants with major protocol deviations.

5. Endpoints

Primary Endpoints:

- Change in dermis density (baseline to 4 weeks).
- Change in LEB thickness (baseline to 4 weeks).

Secondary Endpoints:

- Change in thigh circumference, body composition, cellulite stage, and skin moisture (baseline to 4 weeks and 8 weeks).
- Persistence of dermal changes at 8 weeks.
- Exploratory regression of baseline fat percentage on changes in adiposity and cellulite measures.

6. Statistical Methods

Descriptive statistics (mean, standard deviation, median, interquartile range) will be provided for all continuous variables. Frequencies and percentages will be presented for categorical variables.

Comparisons between groups will be performed using independent samples t-tests (or Mann-Whitney U test if data are non-normal). Within-group changes will be assessed using paired t-tests (or Wilcoxon signed-rank test). Effect sizes (Cohen's d, Hedges' g) will be reported to quantify magnitude of differences.

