For secondary analyses, linear regression will be used to explore associations between baseline body fat percentage and changes in adiposity outcomes. Significance will be set at $p < 0.05$.

7. Handling of Missing Data

Missing data will be evaluated for randomness. If $<5\%$ missing, analyses will be conducted using complete cases. If $>5\%$, multiple imputation methods will be considered. Sensitivity analyses will be performed to assess robustness.

8. Interim Analysis

No interim analyses are planned due to the small sample size and short study duration.

9. Statistical Software

All analyses will be conducted using SPSS version 25.0. Supplementary analyses may be performed using R version 4.3 or later.

10. Reporting

Results will be reported in accordance with CONSORT guidelines. Tables and figures will be used to illustrate changes in primary and secondary outcomes. Effect sizes, confidence intervals, and p-values will be reported.

11. Ethical Considerations

All analyses will be performed on de-identified data. Analyses will adhere to ethical standards and respect participant privacy.

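### The plan states no masking for whoever takes or derives the two ultrasound primary endpoints, so it permits readings made with knowledge of arm and visit

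*Protocol*

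**What the plan says.** The protocol (Study Design) states: "This is a two-arm, parallel-assignment, open-label, randomised controlled trial". SAP 3 repeats this: "This is a two-arm, open-label, parallel-assignment randomised controlled trial with an experimental group (kinesio taping) and a control group (no intervention". On the comparator, the protocol (Intervention) says "Control group participants do not receive any intervention during the study period"; no sham taping is described.

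Both primary outcomes come from ultrasound (protocol, Outcome Measures): "Change in dermis density (measured by high-frequency ultrasound, DermaLab Combo 4" and "Change in low echogenic band (LEB) thickness (measured by ultrasound". SAP 5 sets the interval for each as baseline to 4 weeks, for example "Change in dermis density (baseline to 4 weeks".

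Neither document says who performs the scans, whether a person or the device produces the final values, whether images are kept, or what the measurer knows about arm and visit. No rule is given for probe site, repeat scans or reader reliability. SAP 11 says "All analyses will be performed on de-identified data", but it sits under ethics and is tied to participant privacy. The sensitivity analyses in SAP 7 appear only under missing data.

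**The concern.** With an untreated control arm, anyone who sees participants can readily learn who is taped. If a person decides where the dermis and the low echogenic band begin and end, or chooses the frame to measure, knowing the arm can move the reading. A shift that differs between arms enters the between-group difference directly, and the t-test or Mann-Whitney comparison in SAP 6 cannot separate it from a taping effect. A shift tied to visit but common to both arms cancels in that comparison, but it remains in the within-group paired tests that SAP 6 also plans.

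Nothing else in the plan closes the gap. De-identified records can still carry arm and visit, and reporting to CONSORT (SAP 10) governs description and does not create masking. What is at stake is the interpretation of both primary endpoints.

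**Working it through.** **The plan's own sample size.** The protocol (Sample Size) gives 17 + 17 = 34 in the groups, 38 enrolled and a 10% dropout allowance. 34 / (1 − 0.10) = 37.8, which rounds up to 38, so the dropout step reproduces. The base of 34 cannot be checked, because no effect size, SD or power is given.

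**Inputs for the bias check**
- n = 17 per arm (protocol, Sample Size), so df = 2 × 17 − 2 = 32.
- Independent t-test at 0.05 (protocol, Statistical Analysis; SAP 6). Sidedness is not stated; two-sided is assumed.
- True effect 0.
- b = arm-related shift in mean change, in SDs of the change score. The documents give no value, so b is an assumption and is shown over a range.

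**Formula.** Noncentrality λ = b × √(17/2) = 2.915 b. The critical value is t(0.975; 32) = 2.037. With F the noncentral t distribution function on 32 df,

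P(significant) = 1 − F(2.037; λ) + F(−2.037; λ).

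| b (SD of change) | λ | P(significant), one endpoint |
|---|---|---|
| 0 | 0 | 5.0% |
| 0.2 | 0.583 | 8.7% |
| 0.3 | 0.875 | 13.6% |
| 0.5 | 1.458 | 29.3% |
| 0.7 | 2.041 | 50.8% |
| 1.0 | 2.915 | 80.7% |

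An even chance is reached at b = 0.69. For scale, the smallest observed difference that is significant is 2.037 × √(2/17) = 0.70 SD.

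**Two primary endpoints.** Each is tested at 0.05 and no multiplicity rule is given. If both carry the same shift and are independent, P(at least one significant) = 1 − (1 − P)²:
- b = 0: 1 − 0.950² = 9.8%
- b = 0.3: 1 − 0.864² = 25%
- b = 0.5: 1 − 0.707² = 50%

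In simulation (100,000 runs) with correlation from 0.3 to 0.7 between endpoints, these become about 9.4% to 8.5%, 24% to 20% and 46% to 40%. The 9.8% at b = 0 is a multiplicity effect and a separate matter; only the rise above it belongs to this point.

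**The case against.** The strongest reply is that the mechanism is not in the documents. They name a device for dermis density and say only that LEB thickness is measured by ultrasound. If the device computes the values without human delimitation, there is little for a masked reading to correct. This stands, which is why operator judgement is labelled an assumption here.

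Second, a reader might infer from the open-label label that scans were read unmasked. The documents do not support that. They are silent on the measurer, and masked assessment is possible within an open-label trial. What stands is that the plan permits unmasked reading, and the first thing owed is a statement of what was done.

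Third, a reader might infer from the table that bias probably produced, or would by itself produce, a significant result. The documents give no size for any shift. Any non-zero bias inflates error in any trial, a shift of 0.2 SD takes the rate only to 8.7%, and an even chance on one endpoint needs about 0.7 SD. The table shows sensitivity to an assumed shift and nothing more.

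Fourth, feasibility. The protocol describes enrolment and consent in the past tense, with ethics approval in December 2024 and both documents dated September 2025, so measurements may already be complete. A rule for storing scans prospectively could come too late. This also stands, so the remedy has to work on existing images and needs a fallback.

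The declared open-label design and the pilot label do not answer the point. Masking participants to tape may be impractical, but masking a reader to stored images is a separate step and needs no change of design.

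**Conclusion.** The point holds as a gap in the plan. Both primary endpoints may be derived with knowledge of arm and visit, because neither document states any masking of acquisition, reading or analysis. The possible size depends on an unknown shift: 8.7%, 13.6% or 29.3% false positives per endpoint at 0.2, 0.3 or 0.5 SD, against 5% with none. These figures assume 17 per arm analysed, a two-sided t-test, no true effect, and values that depend on operator judgement. They do not show that readings were unmasked or that any result is biased. The gap is worth closing because it touches both primary endpoints and the remedy is modest where images exist.

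**What to change.** In protocol Outcome Measures and SAP 5, state who acquires the scans, who or what derives the values, and what that person knows of arm and visit. Then add:

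- **Where scans were saved:** each is stored under a random code that carries neither arm nor visit. The existing operator derives dermis density and LEB thickness from the coded scans in random order. The code is opened only after the readings are locked.
- **Where scans were not saved, or the device fixes the value at acquisition:** state who measured and what they knew, report both primary endpoints as unmasked, and qualify the conclusion accordingly.
- **Other outcomes:** report any that was assessed with knowledge of arm as unmasked.

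The cost is some re-reading time for existing staff and a few lines of text, with no extra reader, visit or procedure. Three limits remain and should be stated. Coded reading does not remove bias at image acquisition (probe site, pressure, choice of frame). The same operator may recognise some scans. And it does nothing about participant behaviour in a comparison with an untreated arm.

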Statistical Analysis Plan (SAP)

Official Title:

Clinical Evaluation of Kinesio Taping Outcomes in Stage II Cellulite: A Pilot Randomised Controlled Trial

NCT Number:

NCTXXXXXXX

Document Date:

September 16, 2025

Sponsor/Collaborator:

Klaipėda State University of Applied Sciences (Klaipėdos valstybinė kolegija)

1. Introduction

This Statistical Analysis Plan (SAP) describes the planned analyses for the pilot randomised controlled trial evaluating the effects of kinesio taping on women with stage II cellulite. The SAP defines analysis populations, statistical methods, and reporting conventions in accordance with best practice guidelines.

2. Study Objectives

Primary Objectives:

- To evaluate the effect of kinesio taping on dermis density.
- To evaluate the effect of kinesio taping on low echogenic band (LEB) thickness.

Secondary Objectives:

- To assess changes in thigh circumference, body composition, cellulite stage, and skin moisture.
- To explore persistence of effects at 4 weeks post-intervention.

3. Study Design

This is a two-arm, open-label, parallel-assignment randomised controlled trial with an experimental group (kinesio taping) and a control group (no intervention).

4. Analysis Populations

The primary analysis will be conducted on the intention-to-treat (ITT) population, including all randomised participants who completed at least baseline and one follow-up measurement. Per-protocol analyses may be conducted excluding participants with major protocol deviations.

5. Endpoints

Primary Endpoints:

- Change in dermis density (baseline to 4 weeks).
- Change in LEB thickness (baseline to 4 weeks).

Secondary Endpoints:

- Change in thigh circumference, body composition, cellulite stage, and skin moisture (baseline to 4 weeks and 8 weeks).
- Persistence of dermal changes at 8 weeks.
- Exploratory regression of baseline fat percentage on changes in adiposity and cellulite measures.

6. Statistical Methods

Descriptive statistics (mean, standard deviation, median, interquartile range) will be provided for all continuous variables. Frequencies and percentages will be presented for categorical variables.

Comparisons between groups will be performed using independent samples t-tests (or Mann-Whitney U test if data are non-normal). Within-group changes will be assessed using paired t-tests (or Wilcoxon signed-rank test). Effect sizes (Cohen's d, Hedges' g) will be reported to quantify magnitude of differences.

For secondary analyses, linear regression will be used to explore associations between baseline body fat percentage and changes in adiposity outcomes. Significance will be set at $p < 0.05$.

7. Handling of Missing Data

Missing data will be evaluated for randomness. If $<5\%$ missing, analyses will be conducted using complete cases. If $>5\%$, multiple imputation methods will be considered. Sensitivity analyses will be performed to assess robustness.

8. Interim Analysis

No interim analyses are planned due to the small sample size and short study duration.

9. Statistical Software

All analyses will be conducted using SPSS version 25.0. Supplementary analyses may be performed using R version 4.3 or later.

10. Reporting

Results will be reported in accordance with CONSORT guidelines. Tables and figures will be used to illustrate changes in primary and secondary outcomes. Effect sizes, confidence intervals, and p-values will be reported.

11. Ethical Considerations

All analyses will be performed on de-identified data. Analyses will adhere to ethical standards and respect participant privacy.

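### The week-8 persistence endpoint for the dermal outcomes names no contrast, and the tests on offer allow an uncontrolled reading in which a non-significant result favours persistence

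*SAP*

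**What the plan says.** SAP section 2 has a secondary objective, "To explore persistence of effects at 4 weeks post-intervention". With four weekly tapings, that falls at about week 8. SAP section 5 turns it into the secondary endpoint "Persistence of dermal changes at 8 weeks".

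The other measured endpoints in section 5 are changes over a stated interval. The primary ones follow the pattern "Change in dermis density (baseline to 4 weeks"), and the remaining secondary outcomes are changes from baseline to weeks 4 and 8. Only the week-8 dermal endpoint has no stated contrast.

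SAP section 6 gives two families of test and ties neither to this endpoint:
- For one arm against the other, the text is "Comparisons between groups will be performed using independent samples t-tests (or Mann-Whitney U test if data are non-normal").
- For change inside a single arm, the text is "Within-group changes will be assessed using paired t-tests (or Wilcoxon signed-rank test").

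The significance level is 0.05. Section 6 names no baseline-adjusted or repeated-measures model for the group comparison. Section 10 promises effect sizes and confidence intervals alongside p-values.

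The Protocol's Objectives section says "Secondary objectives include assessing changes in thigh circumference, body composition, cellulite stage, and skin moisture". Neither that section nor the Outcome Measures section mentions week 8 or persistence.

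**The concern.** Persistence of a change can mean at least three things here: the week 4 to week 8 change, the baseline to week 8 change, or the arm difference at week 8. These can give different answers, and the SAP lets the analyst choose after seeing the data.

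One of the permitted choices is a paired week 4 to week 8 test in the taped arm. It has two weaknesses. It leaves out the control arm, so it cannot separate retention of an effect from drift over time. It also reverses the usual burden of proof: a small sample normally makes a favourable claim harder, but here a small sample makes non-significance, and so an apparent finding of persistence, easier.

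Dermis density and LEB thickness are the trial's primary outcomes, so a statement that their changes persisted would be prominent in any report.

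**Working it through.** **Inputs from the documents.** Protocol, Sample Size: "A total of 38 participants were enrolled, with randomisation into two groups (n=17 experimental, n=17 control"). SAP section 6: significance level 0.05, taken as two-sided because sidedness is not stated. Neither document gives an SD, an expected effect or a between-visit correlation.

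**The plan's own figure.** The dropout step reproduces: 34 / 0.9 = 37.8, which rounds up to 38. The 17 per arm cannot be reproduced without an effect size and power. It is consistent with a large effect: a two-sided two-sample t-test with 17 per arm has 80.7% power at d = 1.0. That is the reason for using a 1 SD gain as the illustration.

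**The week 4–8 paired test in the taped arm.** Assume a week-4 gain of 1 SD and a fraction f of it lost by week 8. Let k be the SD of the week 4–8 difference divided by the SD in which the gain is expressed. The test has n − 1 = 16 degrees of freedom, critical value 2.120 and noncentrality f × √17 / k. For f = 0.5 and k = 1 this is 0.5 × 4.123 = 2.06, and the noncentral t distribution gives P(non-significant) = 0.509.

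If the gain is in between-woman SDs and the two visits have equal variance, k = √(2(1 − ρ)), where ρ is the week 4–8 correlation. For comparison, the between-arm t-test on the same week 4–8 change has 32 degrees of freedom and noncentrality f × √(17/2) / k (drift common to both arms cancels).

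| k | implied ρ | Half lost: paired test non-significant | Half lost: between-arm test non-significant | Quarter lost: paired test non-significant |
|---|---|---|---|---|
| 0.447 | 0.90 | 1% | 11.5% | 42% |
| 0.632 | 0.80 | 14% | 39% | 67% |
| 0.8 | 0.68 | 32% | 58% | 77% |
| 1.0 | 0.50 | 51% | 71% | 84% |
| 1.2 | 0.28 | 64% | 78% | 87% |

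The result depends heavily on k. A smaller gain raises the figures: at 0.8 SD, with k = 1 and half lost, the paired test is non-significant 66% of the time.

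**Precision of an interval.** In SDs of the change analysed, the 95% half-width with 17 women is:
- within one arm: 2.120 / √17 = 0.51 SD;
- between arms: 2.037 × √(2/17) = 2.037 × 0.343 = 0.70 SD.

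These are best cases. The analysis set requires only one follow-up measurement, so fewer than 17 per arm may have week-8 data.

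**What baseline adjustment adds.** Assume equal variances and baseline to week-8 correlation r. The variance of the adjusted arm difference, relative to an unadjusted comparison of change scores, is approximately (1 − r²) / (2(1 − r)) = (1 + r) / 2. That is 0.75 at r = 0.5 and 0.90 at r = 0.8: a modest gain that needs no extra data.

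**The case against.** A reader might infer that a within-arm paired test is the only method the SAP offers for change over time. It is not. The between-group tests come first in section 6, the dermal endpoints are change scores, and an independent t-test on change from baseline to week 8 is an ordinary, controlled reading.

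A reader might also infer that the SAP plans to read a non-significant week 4–8 change as persistence. No sentence says so, and no week 4–8 comparison is named. A paired test from baseline to week 8 is equally open, and there non-significance would count against persistence. The promised effect sizes and intervals would help to expose a large loss, and the objective is worded as exploratory, in a pilot.

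The 51% rests on assumed quantities. At week 4–8 correlations of 0.8 or 0.9 it falls to 14% or 1%. Switching to a between-arm test of the week 4–8 change does not cure the problem either, because that test misses the same half loss more often (71% against 51% at k = 1).

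All of this stands, and it limits the point. It does not remove it. The contrast remains unspecified, an interval on a contrast chosen afterwards does not prevent selection, and neither family of tests adjusts for baseline. The between-arm result is also an argument against relying on another significance test, and for reporting a controlled estimate with its interval.

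**Conclusion.** The point holds in this form: persistence is a secondary endpoint without a defined contrast, the tests offered are unadjusted, and one permitted reading has no control comparison and gains support from low power. The Protocol does not carry the endpoint at all.

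Under that reading, with 17 women, a 1 SD gain and half of it lost, non-significance occurs about 51% of the time, and roughly 1% to 64% over the assumptions tabulated. This shows what an undefined endpoint could allow. It is not an estimate of this trial's error rate, and the documents do not support saying that the sponsor intends the uncontrolled reading. Primary endpoints are unaffected. The change is worth making because a better estimate is available from measurements the SAP already plans.

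**What to change.** In SAP sections 5 and 6:
- Define the week-8 endpoint, for dermis density and LEB thickness separately, as the between-arm difference in change from baseline to week 8, adjusted for baseline, with its 95% CI. Use ANCOVA, or a mixed model over weeks 4 and 8 with arm, visit, arm by visit and baseline, which targets the same contrast.
- Report the between-arm difference in week 4–8 change with its 95% CI, labelled descriptive.
- State that a non-significant change, within or between arms, is not evidence of persistence.

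In the Protocol, add the persistence objective and the week-8 dermal endpoint so that the two documents agree. The Protocol already describes enrolment in the past tense, so date the change and say whether any week-8 results had been seen.

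The cost is a few sentences and a standard procedure in the named software, with no new measurements. The downside is that the week 4–8 between-arm contrast is imprecise at this size (half-width about 0.70 SD of the change), so a claim of persistence becomes harder to make.

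### The primary group comparison does not adjust for baseline as a covariate; ANCOVA on the baseline already measured would usually be more precise than the planned t-test at 17 per arm

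*SAP*

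**What the plan says.** SAP section 5 lists the primary endpoints as "Change in dermis density (baseline to 4 weeks") and "Change in LEB thickness (baseline to 4 weeks"). Among the secondary endpoints it lists "Persistence of dermal changes at 8 weeks".

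SAP section 6 gives one method for comparing the arms: "Comparisons between groups will be performed using independent samples t-tests (or Mann-Whitney U test if data are non-normal"). It does not say whether the test is run on change scores or on follow-up values; change scores are the natural inference from section 5. The Protocol's Statistical Analysis section adds only paired t-tests and effect sizes.

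The one regression in the plan is not a treatment comparison: "For secondary analyses, linear regression will be used to explore associations between baseline body fat percentage and changes in adiposity outcomes".

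SAP section 4 makes a baseline measurement a condition of entering the primary analysis population, so the covariate is already to hand. SAP section 10 commits to intervals: "Effect sizes, confidence intervals, and p-values will be reported". The Protocol's Sample Size section ties the planned test to the design: "Sample size was determined using power analysis for an independent t-test, accounting for a 10% dropout rate".

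**The concern.** A t-test on change subtracts the whole baseline value, which amounts to assuming a slope of exactly 1 between baseline and 4-week value. ANCOVA estimates that slope. When the true slope is well away from 1, the change-score comparison carries avoidable noise. If one arm happens to start higher, the change score also over-corrects (slope below 1) or under-corrects (slope above 1).

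With 17 per arm, precision is scarce, and in a pilot the interval for the treatment effect is a main product. What is at stake is the width of that interval for dermis density and for LEB thickness, and how far each result depends on which arm started higher. The validity of the test is not at stake.

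**Working it through.** **Inputs from the documents.** The Protocol's Sample Size section states: "A total of 38 participants were enrolled, with randomisation into two groups (n=17 experimental, n=17 control"). The dropout step reproduces: 34 / (1 − 0.10) = 37.8, rounded up to 38. The 17 per arm cannot be reproduced, because effect size, SD, power and sidedness are not given. Under a two-sided 0.05 test, 17 per arm corresponds to a standardised effect of about 0.99 at 80% power or 1.15 at 90%.

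**Assumed inputs, none of them in the documents.** Standardised effect on the change scale d = 1.0; correlation r between baseline and 4-week value; ratio k of 4-week SD to baseline SD; two-sided test; normal data with the same variance and slope in both arms. With d = 1.0 the t-test has noncentrality 1.0 × √(17/2) = 2.92 on 32 df, giving 80.7% power.

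**Formulae** (baseline SD = 1, N = 34):
- Variance of a change score: 1 + k² − 2rk.
- ANCOVA residual variance: k²(1 − r²), times 1 + 1/(N − 4) = 31/30 for estimating the slope.
- With k = 1 the ANCOVA-to-change variance ratio is (1 + r)/2 × 31/30. At r = 0.5 this is 0.75 × 1.033 = 0.775.
- The interval-width ratio is the square root of the variance ratio, times a factor just above 1 for 31 rather than 32 df.

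**Equal SDs (k = 1), 200,000 simulated trials per setting; t-test on change about 81%:**

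| r | Variance ratio | CI-width ratio | ANCOVA power |
|---|---|---|---|
| 0.3 | 0.67 | 0.82 | 93% |
| 0.5 | 0.77 | 0.88 | 89% |
| 0.7 | 0.88 | 0.94 | 85% |
| 0.9 | 0.98 | 0.99 | 81% |

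The variance break-even is (1 + r)/2 × 31/30 = 1, so r = 29/31 = 0.935.

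**Unequal SDs (k = 1.25).** ANCOVA power is 88.0, 83.8, 80.1, 79.3 and 81.4% at r = 0.3, 0.5, 0.7, 0.8 and 0.9, against about 80.7%. So there is a gain at 0.3 to 0.5, none at 0.7, a loss of about 1 point at 0.8, and under 1 point of gain at 0.9. The worst case is rk = 1, where the true slope is 1. Both variances then equal k² − 1, and ANCOVA pays the factor 31/30 for nothing: 79.3% against 80.6%, with an interval 1.7% wider. Across effect sizes the largest loss is about 1.5 points, at d = 0.85.

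**Chance baseline gaps (no effect, k = 1).** The SE of the baseline gap is √(2/17) = 0.343 SD, so a gap above 0.5 SD occurs in about 14.5% of randomisations. Given a gap g, the expected change-score difference is (r − 1)g instead of zero.

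| r | Type I error, gap > 0.5 SD | Type I error, otherwise | Weighted total |
|---|---|---|---|
| 0.3 | 15.7% | 3.2% | 0.145 × 15.7 + 0.855 × 3.2 = 5.0% |
| 0.5 | 12.2% | 3.8% | 0.145 × 12.2 + 0.855 × 3.8 = 5.0% |
| 0.7 | 9.6% | 4.4% | 0.145 × 9.6 + 0.855 × 4.4 = 5.2% |
| 0.9 | 6.4% | 4.8% | 0.145 × 6.4 + 0.855 × 4.8 = 5.0% |

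The totals are 5% within rounding and simulation error. ANCOVA is at about 5% in the large-gap subset and overall.

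**Non-normal follow-up residuals (assumed shapes; d = 1.0, k = 1, 40,000 trials per setting).** Power of Mann-Whitney on change / ANCOVA:

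| r | Lognormal (log-SD 1) | t with 3 df |
|---|---|---|
| 0.3 | 93 / 91% | 88 / 93% |
| 0.5 | 95 / 90% | 90 / 91% |
| 0.7 | 98 / 87% | 92 / 88% |
| 0.9 | 99 / 85% | 94 / 85% |

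Mann-Whitney leads by about 4 to 14 points at r of 0.7 or more, and by about 6 at r = 0.5 under the lognormal (before rounding). In the same runs ANCOVA matched or beat the change-score t-test. Mann-Whitney was run directly, not after a normality test.

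**The case against.** The strongest case for leaving the plan alone has four parts.

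- **The planned test is sound.** It is unbiased under randomisation, holds its 5% level, and matches the test behind the sample size. This stands. A reader might infer from the large-gap type I error that the t-test is invalid or biased. The documents and the arithmetic do not support that: the excess in about 14.5% of randomisations is balanced by slight conservatism in the rest.
- **Baseline is not ignored.** A change score subtracts it. This also stands. A reader might infer that there is no baseline adjustment of any kind; the supportable statement is that baseline is not a covariate.
- **The plan has a rank-based fallback.** Under strong skew or heavy tails, replacing it with ANCOVA could cost more power than ANCOVA gains elsewhere. This stands, and it is why the rank test should be kept. ANCOVA does not settle the undefined trigger for non-normality. It does still give the adjusted mean difference and interval, which a Mann-Whitney p-value alone does not.
- **It may be too late.** The Protocol describes enrolment in the past tense. The documents are dated 16 September 2025, 263 days (263/7 = 37.6 weeks) after ethics approval on 27 December 2024, against 8 weeks of follow-up per participant. One might infer that outcomes had been seen, but the documents do not say so. Nor can it be claimed that the change would fix the model in advance.

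The gain also rests on unstated inputs, so no figure above is this trial's actual power.

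**Conclusion.** The point holds as an optional improvement in precision, with medium confidence. Under near-normal data and equal SDs, ANCOVA gains about 12, 8, 4 and less than 1 points of power at r = 0.3, 0.5, 0.7 and 0.9, and narrows the interval by 18, 12, 6 and 1%. At an SD ratio of 1.25 the gain is confined mainly to r of 0.5 or below. The loss against the t-test under normality is at most about 1.5 points, which is why usually is the right strength of claim. Against Mann-Whitney under marked non-normality the balance can go the other way by a wider margin.

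The conclusion rests on the t-test being applied to change scores, on 17 analysed per arm, and on the assumed d, r and SD ratio. The Protocol gives 38 enrolled and 17 + 17 = 34 in the groups; 19 per arm would not materially change the result.

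**What to change.** In SAP section 6, estimate the treatment effect for each primary endpoint by ANCOVA of the 4-week value on arm and baseline value, and report the adjusted mean difference, 95% CI and p-value. Use the same model for the continuous secondary endpoints and the 8-week values, but not for cellulite stage, which is ordinal. State that the planned t-test and Mann-Whitney test are run on change scores and report them alongside. If residuals are clearly non-normal, retain a rank-based test rather than dropping it.

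Date the amendment and state whether any outcome data had been seen. If they had, keep the planned test primary and label ANCOVA as a disclosed supplementary analysis.

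The cost is one degree of freedom, the possible power losses given above against the t-test and against Mann-Whitney, and possible post hoc status. No new data or software are needed.
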